Low-contrast visual acuity (LCVA) is a sensitive measure of visual impairment in MS patients (40) and has been recommended for incorporation into the Multiple Sclerosis Functional Composite (MSFC). LCVA is correlated with retinal nerve fiber layer thickness as measured by OCT (41) (see section 5.F., below). Visual acuity will be measured in each eye separately as well as binocularly, at three contrast levels (100%, 2.5%, and 1.25%) using low-contrast Sloan letter charts (Precision Vision, LaSalle IL). For each measurement, the number of letters (maximum = 70) correctly identified will be recorded. Changes in LCVA over the study, and correlation of LCVA measures with OCT measures, will be exploratory outcomes of the study.

E. Fatigue

Fatigue is an extremely common symptom in MS patients, and often one of the most disabling. Over 50% (and up to 90%) of MS patients cite fatigue as a significant problem (42). The Fatigue Severity Scale (FSS) is a validated, patient-reported metric of fatigue symptoms that was specifically developed for MS and related disorders (43). The FSS will be administered to all study subjects at baseline and at each annual follow-up. The change in FSS from baseline to study end will be compared between treatment arms, as an exploratory endpoint. Many MS patients are treated with stimulant medications (such as methylphenidate, modafinil, or amphetamine preparations) for fatigue symptoms, and such medications (and the timing of their dosing) could obviously affect FSS scores, as well as other study measures. Accordingly, subjects will be asked not to take such stimulant medications on study visit days (although they will be advised to bring such medications with them, so that they may take them as needed after the study assessments are completed).

F. Global Measures of MS-related disability (EDSS and MSFC)

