Multiple linear regression models will be used to test for between group differences in LCVA scores adjusted for other covariates. Binocular LCVA scores will be used to test for a treatment effect on vision changes; monocular LCVA scores will be used for correlation with OCT measures (from the matching eye). Generalized estimating equation (GEE) models will be used to test for between group differences in change over time in vision loss rates adjusted for other covariates. In addition correlation of LCVA with OCT measures (RNFL and macular volume) will be evaluated using Pearson correlation analysis (Spearman correlation will be used if measures have skewed distributions).

Between group differences in mean OCT macular volume scan measures will be tested using multiple linear regression models adjusted for covariates. mixed model analyses of repeated measures will be used to test for between group differences in change over time in OCT macular volume measures.

7. Study Procedures

A. Schedule of study procedures:

1. Symptoms questionnaire for subjective adverse events at baseline, 3, 6 and 12 months and then annually.
2. Comprehensive metabolic panel (CMP) and hemoglobin A1C (HbgA1C) at screening, 6 and 12 months, and then annually.
3. EDSS and DEXA scan (both hips/femurs and lumbar spine) at screening and then annually.
4. OCT at baseline and then annually.
5. MSFC, T25FW, 6MWT, LCVA, MSWS-12, AI, FSS and BRB-N at baseline and then annually.
6. Practice sessions (at screening visit:
 - a. BRB-N - 1 practice session

- b. PASAT - 2 practice sessions (in addition to the one administered during BRB-N)
- c. 9HP - 3 practice sessions

Table 1. Study Schedule

	V1 Screen 0 to -4 wks	V2 Baseline M0	V3 *** M3	V4 M6	V5 M12	V6 M18	V7 M24	V8 M30	V9 M36
Informed Consent	X								
Inclusion/Exclusion	X								
Injection Training		X							
Blood Pressure		X	X	X	X	X	X	X	X
Weight		X	X	X	X	X	X	X	X
Safety Lab Tests^a	X			X	X		X		X
Skin & Edema Assessment		X	X	X	X	X	X	X	X
OCT		X			X		X		X
LCVA		X			X		X		X
EDSS	X				X		X		X
Timed 25-Ft Walk		X			X		X		X
9-Hole Peg Test	XXX	X			X		X		X
PASAT (apart from BRB-N)	XX								
6 Minute Walk Test		X			X		X		X
MS Walking Scale - 12		X			X		X		X
Fatigue Severity Scale (FSS)		X			X		X		X
Hauser Ambulation Index		X			X		X		X
Brief Repeatable Battery	X	X			X		X		X
DEXA Scan^b	X ^c				X		X		X
Randomization		X							
Symptom Questionnaire		X	X	X	X	X	X	X	X
Concomitant Medications		X	X	X	X	X	X	X	X

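### The LCVA and macular volume endpoint regressions name no baseline value, and LCVA change over time rests on an undefined vision-loss outcome

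*Combined protocol and SAP*

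**What the plan says.** Section 5.D (Vision) has acuity measured in each eye and binocularly at three contrast levels, and "the number of letters (maximum = 70) correctly identified will be recorded". The role of the measure is set there too: "Changes in LCVA over the study, and correlation of LCVA measures with OCT measures, will be exploratory outcomes of the study". Section 5.G makes change in macular volume exploratory as well. Section 7.A and Table 1 schedule LCVA and OCT at baseline and then annually.

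The analysis is in Section 6.E, under Other vision measures:

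- LCVA, regression: "Multiple linear regression models will be used to test for between group differences in LCVA scores adjusted for other covariates". Binocular scores carry the treatment comparison.
- LCVA, over time: GEE models for "between group differences in change over time in vision loss rates adjusted for other covariates".
- Macular volume, regression: "Between group differences in mean OCT macular volume scan measures will be tested using multiple linear regression models adjusted for covariates".
- Macular volume, over time: "mixed model analyses of repeated measures will be used to test for between group differences in change over time in OCT macular volume measures".

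The general covariate list earlier in Section 6.E is age, gender and MS phenotype, with EDSS and disease duration added if significant. It contains no baseline value of the outcome.

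**The concern.** In a randomised trial, leaving out the baseline value does not bias the comparison, but it leaves stable differences between subjects in the error term. Acuity and macular volume are measured before treatment in every subject, so the information to remove that variation will already be on file. Elsewhere in Section 6.E the plan uses it.

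The longitudinal LCVA analysis raises a second issue. A score recorded in letters is replaced by a vision-loss outcome for which no section gives a letter threshold, a contrast level or a confirmation rule. If a yes/no event is meant, cutting the score discards information. It also leaves the cut-off and the contrast level to be chosen later, in a plan that makes no multiplicity adjustment.

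**Working it through.** **Side by side (Section 6.E)**

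| Outcome | Baseline named in the endpoint regression? | Change over time |
|---|---|---|
| 6MWT, MSWS-12, AI, BRB-N, MSFC | Yes | Mixed model |
| RNFL, temporal quadrant | Yes for change; not for the three-year rate of change | Mixed models |
| FSS | Yes | Mixed model |
| LCVA | No | GEE on vision loss rates |
| Macular volume | No | Mixed model |

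GEE is planned for three outcomes. Two have a defined event: 20% worsening of T25FW (Section 5.A) and EDSS progression (Section 5.F). The third, vision loss, has none.

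**The plan's own figure.** No sample size is given for LCVA or macular volume. The only one is 42 per arm for T25FW (Section 6.B: 0.6 against 0.3, two-sided 0.05, 80% power). It reproduces with pooled variance and no continuity correction: [1.96 × √(2 × 0.45 × 0.55) + 0.8416 × √(0.6 × 0.4 + 0.3 × 0.7)]² / 0.3² = 41.97, so 42. I use 42 per arm below only as a realistic group size.

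**Assumptions, none of them in the documents.** Baseline to follow-up correlation r of 0.6 to 0.8; equal SD at both times; a true effect of 0.5 SD; normal scores.

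**Residual variance, as a fraction of the follow-up variance.** Raw follow-up score: 1. Change score: 2(1 − r). Baseline-adjusted: 1 − r². The adjusted-to-change ratio is (1 − r²) / [2(1 − r)] = (1 + r)/2.

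| r | Adjusted, 1 − r² | Saving against raw score | Equivalent subjects, 1/(1 − r²) | Adjusted ÷ change, (1 + r)/2 | Saving against change score |
|---|---|---|---|---|---|
| 0.6 | 0.64 | 36% | 1.6 times | 0.80 | 20% |
| 0.7 | 0.51 | 49% | 2.0 times | 0.85 | 15% |
| 0.8 | 0.36 | 64% | 2.8 times | 0.90 | 10% |

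Against a change score, the equivalent gain in subjects is 1/0.80 = 1.25 times down to 1/0.90 = 1.11 times.

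**Power at 42 per arm**, Φ(0.5 × √(42/2) / s − 1.96), where s is the square root of the residual variance:

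- Raw score (s = 1): Φ(2.291 − 1.96) = 63%.
- Change score: 73%, 84% and 95% at r = 0.6, 0.7 and 0.8.
- Baseline-adjusted: 82%, 89% and 97%.

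Simulation with 4,000 trials per setting agreed: at r = 0.7 and 0.8, about 62% unadjusted, 83% and 94% for change, and 89% and 96% adjusted.

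**If vision loss is a yes/no cut of the score.** The efficiency relative to the uncut score is φ(c)² / [p(1 − p)], where p is the control-group event rate and c its normal cut-point. It is 0.34, 0.49, 0.58 and 0.64 at p = 10%, 20%, 30% and 50%. With a 0.5 SD shift and 42 per arm, power at one visit is 20%, 30%, 36% and 43%, against 63% for the uncut score.

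**The case against.** The case for leaving this alone has several parts, and much of it stands.

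- **Macular volume is mostly covered.** Its repeated-measures mixed model keeps the measure continuous and tests change over time. The FSS mixed model names no baseline term either, so there is nothing to bring into line. The point reaches only the macular volume endpoint regression.
- **The plan is less uniform than it looks.** A reader might infer that these outcomes alone depart from a standard used everywhere else. The text does not support that. Weight, blood pressure, HgbA1c and bone density changes are compared by t-tests, the RNFL rate-of-change regression names no baseline thickness, and the cytokine models in Section 8 list none among their example covariates.
- **The binary reading is an inference.** The LCVA sentence closely follows the one on EDSS progression rates, which makes a yes/no event plausible. But the plan also uses the word rate for continuous RNFL change, and GEE can be fitted to a continuous score. What is established is that the outcome is undefined, so the efficiency loss from a cut is conditional.
- **The larger variance saving assumes raw scores.** Section 5.D speaks of changes in LCVA. If a change score is regressed, part of the baseline information is already used. Section 6.E says scores, so both figures must be shown. Age, gender and phenotype are already in the model, so r should be read as the correlation left after them.
- **A responder analysis is not wrong in itself.** T25FW and EDSS are handled that way. A vision-loss analysis can stay as a supplement once it is defined.

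The missing baseline term may simply be a drafting omission. It still needs correcting, because the regression as written does not contain it.

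**Conclusion.** The concern holds as a minor, cost-free improvement to two exploratory outcomes. The LCVA and macular volume endpoint regressions name no baseline value, while the walking, cognition, MSFC, RNFL-change and FSS regressions do. The gain from adding it is a 36-64% cut in residual variance if raw follow-up scores are analysed, or 10-20% if change scores were intended. Both ranges rest on an assumed r of 0.6 to 0.8. The power figures also rest on an assumed 0.5 SD effect.

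The GEE outcome for LCVA needs a definition or a replacement, because "change over time in vision loss rates adjusted for other covariates" cannot be computed from the plan as written. It would go too far to conclude that the plan certainly dichotomises the score, that the macular volume mixed model is deficient, or that any secondary or primary result is at risk. The documents support none of these.

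**What to change.** In Section 6.E, under Other vision measures:

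1. Add baseline binocular LCVA, at the same contrast level as the outcome, to the LCVA regression, and baseline macular volume to the macular volume regression. State which contrast level or levels are tested.
2. Test LCVA change over time on the 0-70 binocular letter score, with the repeated-measures mixed model already planned for FSS and macular volume.
3. If a vision-loss analysis is kept as a supplement, fix its letter threshold and contrast level in advance.
4. Leave the macular volume mixed model as it is.

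The cost is a few lines of SAP wording. No new data, visits or subjects are needed.

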2. Extrapolated to a 3 year follow up period, 60% of progressive MS patients will show a 20% or greater increase in T25FW.

Utilizing a significance level of 0.05 and equal sample sizes, 42 subjects per treatment arm would provide 80% power to detect a 50% difference in the proportion of subjects reaching the threshold of 20% worsening in T25FW ($P1 = 0.6$, $P2 = 0.3$, $\alpha = 0.05$, $\beta = 0.2$, 2-sided test). Given the length of the study, we anticipate a dropout rate of up to 10-20% of randomized subjects. To account for this possibility, a total sample size of 100 subjects (50 per treatment arm) will be randomized.

C. Randomization

The study will utilize blocked randomization stratified by study center, with equal (1:1) allocation to the ACTH and control groups.

D. Blinding

Study subjects, their referring physicians, the study monitor, and all study personnel who come in contact with study subjects (including site principal investigators, examining neurologists, study coordinators, nurses, and other study staff and their designated backups) will be blinded to treatment allocation. One investigator who will not come in direct contact with study subjects ([name]) as well as the study statistician and other members of the Data Safety Monitoring Board (DSMB, see section 7F) will be unblinded, to allow for assessment of any safety concerns that may arise over the course of the study.

E. Data Analysis Plan

Descriptive analyses of baseline characteristics and all outcome measures (primary and secondary) will include means with standard deviations or medians with ranges for continuous variables depending on the parametric or non-parametric distribution of the variables, and frequencies with percentages for categorical variables. Between group (ACTH and placebo) comparisons of baseline characteristics and baseline outcome measures will be done using two sample t-tests or Wilcoxon rank sum tests for parametric and non-parametric continuous variables, respectively, and Chi-square tests or Fisher's exact tests for categorical variables.

Models will adjust for age, gender, and MS phenotype; EDSS and disease duration will be included as covariates if significant in preliminary models. Interactions between treatment group and MS phenotype will be tested in each model; if significant, treatment effect will be evaluated in models stratified by MS phenotype.

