Subjects will be asked to contact their study site if they develop new symptoms that are concerning to them. The local study coordinator will record the reported symptoms on the Unsolicited AE Form, which will be reviewed by the local investigator. An unscheduled study visit will occur if the local investigator deems these AEs as potentially serious, possibly related to study medication, and/or requiring in-person assessment. If the reported symptoms are interpreted as mild and/or unrelated to study medication, the subject may be referred to their primary physician or advised to report back by phone with updates about symptom

evolution/resolution. Unscheduled visits will not be routinely performed for suspected MS relapse (see section 7D, Relapses), although they may occur in this situation if the reported symptoms are interpreted as a possible treatment-related AE. Assessments/procedures performed at an unscheduled visit will include all of the assessments done at Visit 3 (see Table 1) with the exception of study drug distribution; any further assessments and/or procedures (e.g. physical examination, other tests, referrals) will be done at the discretion of the local investigator.

F. Early Termination and Intent to Treat

Once subjects are randomized, regardless of if or the length of time they have been on blinded treatment, they will be included in the efficacy (intent to treat) analysis if efficacy data are available (that is, if they have completed at least one annual follow-up visit). Subjects who withdraw (e.g., due to side effects) prior to completing the Month 12 visit will be asked to return the study drug to the site, and to participate in annual phone calls (Months 12 and 24), and to return to the site for the final visit at Month 36. Subjects who withdraw after completing the Month 12 visit will be asked to return the study drug to the site, and to complete the remaining annual study visits (i.e., Month 24 and Month 36) even though they are not receiving drug. Subjects are of course allowed to decline further participation, in which case they would be considered lost-to-follow-up.

G. Data Safety Monitoring

A DSMB will be formed and will consist of one MS specialist, one neurologist familiar with the evaluation and treatment of MS but not otherwise associated with the study, and the study biostatistician. A DSMB chairperson will be chosen from one of the two neurologists on the DMSB.

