Safety data will be reviewed by the DSMB at 6 and 12 months and then annually, starting from the time the first subject receives a dose of study medication and ending at participant study completion (i.e., no active participants on study drug and enrollment closed). Reports from all DSMB meetings will be forwarded to the Institutional Review Board (IRB). Any SAEs or unexpected AE's reported at other times will be reviewed by the head of the DSMB and reported to other members of the DSMB if considered significant enough to warrant interim review by the full committee. In the event of unanticipated SAEs that reflect new or increased risk to the subjects and are considered possibly related to the study medication or procedures (UPIRTSO) the funding sponsor and all study sites will be notified within 48 hours of the local investigator learning of the event. The local IRB will be notified within that IRB's policy timelines (e.g., the University of Minnesota IRB will be notified within 10 business days). A detailed analysis of all AEs will be conducted at the end of the first year of the study. The efficacy measures will also be analyzed annually throughout the study to see whether any signal of benefit is appearing. However, the study will be terminated only if there are unacceptable adverse events, not because of lack of any efficacy signals since it may take the entire 3 year duration of the study for any

beneficial effect to become manifest. Study termination due to safety concerns will be at the discretion of the DSMB; no pre-specified stopping rules will be used.

8. Cytokine sub-study

There are multiple mechanisms by which melanocortins such as adrenocorticotrophic hormone (ACTH) might alter the course of multiple sclerosis (MS) in a beneficial way (16, 54). One such mechanism is altering the balance between pro-inflammatory and anti-inflammatory cytokines via direct immunomodulating effects of melanocortins on immune system cells. A sub-study will be performed (at the University of Minnesota site only) to evaluate the change in plasma cytokine levels in subjects receiving ACTH compared to those receiving placebo, in order to better elucidate the possible mechanisms of ACTH in MS.

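### Yearly efficacy analyses have no stated audience or permitted decision, and the unblinded study statistician could see the treatment trend before the final models are fixed

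*Combined protocol and SAP*

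**What the plan says.** **The looks (section 7.G, Data Safety Monitoring).** "The efficacy measures will also be analyzed annually throughout the study to see whether any signal of benefit is appearing". The next sentence limits what can follow: "However, the study will be terminated only if there are unacceptable adverse events, not because of lack of any efficacy signals". Safety termination is left to the DSMB's discretion, and "no pre-specified stopping rules will be used".

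**Who is unblinded (section 6.D, Blinding).** "One investigator who will not come in direct contact with study subjects", "as well as the study statistician and other members of the Data Safety Monitoring Board", "will be unblinded, to allow for assessment of any safety concerns that may arise over the course of the study". Safety is the only reason given. Section 7.G makes the DSMB two neurologists "and the study biostatistician".

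**What is still open (section 6.E, Data Analysis Plan).** Age, gender and MS phenotype are fixed covariates. Beyond these, "EDSS and disease duration will be included as covariates if significant in preliminary models". Treatment effects are estimated within phenotype if the interaction is significant. Models are run with and without subjects whose therapy changed mid-study, and everyone is kept if the two agree. Time to progression uses Cox models or Kaplan-Meier, depending on whether the Cox assumptions hold. No date is given by which these choices must be settled.

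**The concern.** A yearly search for benefit in a placebo-controlled trial implies comparing the arms, although the text does not say so outright. Section 7.G gives the DSMB safety data to review. It names nobody to run or receive the efficacy analysis, describes no closed report, and sends reports of all DSMB meetings to the IRB without separating open from closed content.

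The plan mentions no statistician other than the one on the DSMB. The person best placed to settle the open points in section 6.E may therefore have seen the treatment trend for years. Earlier annual results come from the same subjects as the 36-month result, so the trend says something about which choice would favour which conclusion. At stake is whether the final p-value can be defended as coming from an analysis chosen without knowledge of the results.

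**Working it through.** **1. The plan's own figure.** Section 6.B gives 42 per arm for 0.60 versus 0.30, two-sided 0.05, 80% power. With pooled variance and no continuity correction:

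n = [z(0.975)·√(2·p̄·(1−p̄)) + z(0.80)·√(p₁(1−p₁) + p₂(1−p₂))]² / (p₁−p₂)²

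with p̄ = 0.45:

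n = [1.960·√0.495 + 0.842·√0.450]² / 0.09 = [1.379 + 0.565]² / 0.09 ≈ 42

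Power at 42 per arm is 0.800. The figure reproduces and assumes a single final test.

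**2. Do the looks raise the error of that test?** Under the null, the final statistic is standard normal whether or not anyone computed earlier ones. A simulation of 1,000,000 paths of Z(t) = B(t)/√t, rejecting only if |Z(1)| > 1.96, gave 0.0496, 0.0499 and 0.0503 with three, four and five equally spaced looks. The looks alone cost no alpha.

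**3. What remains open in section 6.E.**

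| Choice | Rule in the plan | What is undefined |
|---|---|---|
| EDSS, disease duration | Enter if significant | The level, and what the preliminary models contain |
| Phenotype stratification | If the interaction is significant | The level, and which result then leads |
| Subjects with changed therapy | Keep all if the two models agree | What counts as agreement, and what happens otherwise |
| Time to progression | Cox or Kaplan-Meier | How the assumptions are judged |

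The primary model is partly fixed: logistic regression at 36 months with age, gender and phenotype.

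**4. What free choice among such models could do.** This is an illustration with assumed inputs, not a forecast. Null data were simulated for 42 per arm, with an event probability of 60% at average covariate values in both arms. EDSS and duration had log-odds effects of 0.3 or 0.6 per SD (approximate for duration), and 10% or 20% of subjects were regimen changers at random. Eight models were fitted: EDSS in or out × duration in or out × changers in or out. There were 2,000 runs per setting.

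| Changers | Log-odds | One fixed model | Smallest p of eight |
|---|---|---|---|
| 10% | 0.3 | 0.0485 | 0.0905 |
| 10% | 0.6 | 0.0500 | 0.1000 |
| 20% | 0.3 | 0.0445 | 0.0930 |
| 20% | 0.6 | 0.0530 | 0.1075 |

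Monte Carlo standard errors are √(0.05·0.95/2000) = 0.005 and √(0.10·0.90/2000) = 0.007. Phenotype stratification and the time-to-event choice were not included.

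**5. Timing.** In Table 1, T25FW and the other efficacy measures are first repeated at Month 12. The Month 6 DSMB review in section 7.G covers safety data, so no repeat efficacy measurement exists by then for the first subject.

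**The case against.** **The looks do not create the looseness.** Section 6.E gives rules, not a free menu, and they would be just as data-driven at the final analysis if the yearly looks were deleted. This stands. The best-of-eight figures assume a selection the plan does not authorise, and they do not depend on any interim look. What the looks add is a chance to see the trend while the undefined parts of the rules are still unsettled. That is why the models need fixing whether or not the looks stay.

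**A DSMB may need efficacy data.** Whether adverse events are unacceptable can reasonably depend on benefit, and 7.G leaves that judgement to the DSMB. This stands, so the looks cannot be called useless. But the purpose the plan states is to watch for benefit, not to weigh benefit against harm.

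**Silence is not disclosure.** The sentence sits in the data safety monitoring section and may be meant for the DSMB alone. This is fair: the plan fails to say who sees the results; it does not say that they are circulated.

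**Existing blinding limits leakage.** A reader might infer that the unblinded investigator will receive efficacy results, or that leaked trends will alter retention or co-treatment. The documents do not support either. They unblind that investigator for safety and neither grant nor exclude access to efficacy output. Subjects, referring physicians, the study monitor and site staff in contact with subjects are blinded, and no leak route is shown.

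**Conclusion.** The point holds as an avoidable risk of operational bias and informed model selection. It rests on two readings: that looking for benefit means comparing arms, and that the study statistician, as an unblinded DSMB member, could see the comparison. The first is a strong inference; the second follows from the stated roles, although no text assigns the analysis.

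The size cannot be calculated from the documents. The range of about 0.09 to 0.11 shows what unrestricted choice among eight models could do under the stated assumptions. It is a worst case for that set, not an expected error rate.

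A reader might also infer that three yearly tests at 0.05 raise the type I error to 10.7%. That describes claiming success at whichever look is significant. The plan tests the primary outcome at 36 months, rules out termination for anything but adverse events, and gives neither the number of looks nor their information fractions. The figure does not apply to this trial.

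**What to change.** 1. In section 7.G, delete the yearly between-arm efficacy analysis, or confine it to a closed DSMB report used only for benefit-risk judgement. If it is kept, name who prepares and who receives it, and keep its content out of reports that leave the DSMB.
2. In either case, sign the final covariates, models and analysis sets before the first between-arm efficacy analysis. Since efficacy is first repeated at Month 12, the lock should precede any comparison of Month 12 data. It is needed even if the looks are dropped, because the statistician remains unblinded. It should say whether EDSS and disease duration are in or out, how the phenotype interaction is tested and reported, which subject set is primary when therapy changes, and which time-to-event method is used.
3. In section 6.D, state that the unblinded investigator does not receive efficacy results or take part in analysis decisions.

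The cost is protocol wording: no alpha, and still 42 evaluable subjects per arm and 100 randomized. The sponsor and investigators give up an informal early view of benefit outside the DSMB and some freedom to choose models from the data.
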